This Phase I feasibility study will evaluate surgery- and device-related safety in a small number of pediatric (n=10, aged 2 to 6 years) non-NF2 subjects, who are either not currently benefitting from a CI or who have radiological evidence of cochlear nerve deficiency, cochlear aplasia, or post-meningitis complete cochlear ossification. Currently, a CI is the device of choice if there is a cochlea into which a CI can be placed. To be included in this study, there must be evidence the CI has not provided auditory benefit (thresholds below the level of conversational speech and absence of pattern perception). Because the ABI will not be implanted before the child is 2-years-old, a child who receives a CI at age 1 year and who is tracked for 6-12 months, will be evaluated to determine CI benefit. This time frame still enables the child with a CI to take advantage of a sensitive period for auditory and linguistic development with an ABI. Enrolled subjects must have all screening evaluations performed prior to surgery and must meet all inclusion and exclusion criteria. The Principal Investigators will review the results of all screening assessments to determine subject eligibility. In addition, the subject's parents or legal guardians must be thoroughly informed about the study, including the study visit schedule, and required evaluations. The written informed consent must be obtained from the parents or legal guardians prior to enrollment.

Inclusion criteria for subjects with and without a CI:

- Age 2 to 6 years of age (24 months to 72 months)
- Bilateral profound sensorineural hearing loss as documented through behavioral assessments
- A diagnosis of one of the following, based on thin-slice MRI and CT
 - o Cochlear aplasia
 - Complete cochlear ossification, post meningitis
 - Cochlear nerve deficiency (aplasia, hypoplasia)
- Strong family support, to include language proficiency of both parents/legal guardian(s) in the child's primary mode of communication and primary educational mode of communication(e.g.,

English) or another form of visual support for communication (e.g., American Sign Language, Signed English, or Cued Speech)

- Reasonable expectations from parents, to be determined informally by clinicians and psychologist, including
 - Understand benefits and limitations of auditory brainstem implant
 - Understand parental role in rehabilitation

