 - Understand the child may not be successful in developing spoken language as a primary mode of communication or in developing sufficient oral language skills to allow maximum academic progress in an oral environment
- The child's parents/legal guardians have proficiency in spoken and written English to enable completion of study-related questionnaires
- Informed consent from the child's parents/legal guardian

Inclusion Criterion for subjects with a CI

 Lack of audiological benefit from the implant, at 12 months post-implant(e.g., Neural Response Telemetry, evoked cortical responses, or behavioral responses)

Inclusion Criteria for subjects without a CI

- Lack of audiological benefit after a three month appropriate amplification trial, except for:
 - o Post-meningitis subjects with CT evidence of complete ossification
 - o CT evidence of cochlear aplasia or cochlear nerve deficiency

Exclusion Criteria

- Cognitive and/or developmental delays which would be expected to interfere with the child's ability to cooperate in testing and/or device programming, in developing speech and oral language, or which would make an implant and subsequent emphasis on aural/oral communication not in the child's best interest
- Anomaly/pathology involving the brainstem and/or cortex
- Retrocochlear pathology resulting from NF2, or other types of cranial nerve/brainstem tumors
- Co-existing medical conditions that require irradiation of the brainstem and/or auditory cortex
- Any medical contraindication, such as
 - o Cardiopulmonary or renal disease precluding safe administration of general anesthesia

Protocol Overview

Preoperative baseline measures will include documentation of a diagnosis of cochlear nerve deficiency, cochlear aplasia or complete ossification, with the standard audiological test battery showing lack of 12-month benefit for subjects with a CI. Following surgical implantation of the investigational device and a 4-to-6 week period of healing, the ABI will be activated at CHLA. Programming of the speech processor (mapping) will occur at the USC Caruso Family Center for Childhood Communication and the map will be adjusted and auditory performance assessed at six intervals: device activation, and at 1, 3, 6, 9, and 12 months post-activation. Subjects will be evaluated using an FDA-approved (for NF2 cases) Nucleus speech processor and programmed with an FDA-approved sound processing strategy. A summary of the visit schedule is shown in Table 1.

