Each prospective subject's parents/legal guardians will be informed of the nature of the study and the potential risks. Informed consent will be obtained from the parent/legal guardian prior to performing any study-related screening procedures. Review of medical history, MRI and/or CT, pre-surgical evaluations, audiological evaluation, and speech language pathologist assessment. To optimize scheduling convenience for the subject and for the investigational staff, these screening procedures may be performed on more than one day. The screening examinations may take place up to 3 months

(12 weeks) prior to surgery. Screening examinations may be repeated at the discretion of the Principal Investigators.

Neurotology Examination. Prior to surgery, [name] will conduct a neurotologic examination at CHLA. One week (±1 day) after the subject is released from the hospital, he will conduct a follow-up examination. He will assess the status of the incision, facial nerve function, and the implanted ear. [name] will repeat the neurotology examination at Visits 7 and 10, in conjunction with the audiology/device programming visits.

Table 1. Phase I evaluation and visit schedule

Visit #	1	2	3	4	5	6	7	8	9	10	11-12
		Day 0	Day 1-	Wk 1	Wk 4-6	M 1	М 3	M 6	M 9	M 12	Yr 2-3
Activity	Scre en	Impla nt	In- hospit al		Activ ate devic e	Device Fitting/Evaluation					Early Efficacy
Informed consent	Х										
Medical History	Х										
Audiological tests	Х										
Psychological tests	Х										
Vital signs	X	X	X		X						
Physical examination	X										
Chest x-ray, EKG	X										
Vaccinations	X										
CT and MRI	X										
Laboratory tests	Х										
Neurotology exam	Х			Х			Х			Х	
EABR		Х			Х						
Soundfield Thresholds						Х	X	X	Х	X	X
Monitor vital signs					Х	Х	X	Х	X	X	X
Device Fitting ("Mapping")					Х	Х	X	Х	Х	Х	X
IT-MAIS/MAIS	X					Х	Х	Х	Х	X	
Adverse Events		X	X	Χ	X	Х	Х	Х	X	Χ	X
Communication Battery										X	X

Medical History and Examination: ABI candidates will undergo a comprehensive examination by the pediatric anesthesiologist at CHLA to evaluate for coincident medical problems involving the cardiopulmonary, neurological, ophthalmological, renal, and hematologic systems. Coincident medical

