Diagnostic Imaging. All subjects selected for ABI will have already been studied by CT and MRI in order for a diagnosis of cochlear nerve deficiency, complete cochlear ossification, or absence of a cochlea, or for a CI. The CT provides detailed information about the petrous bone and cochlea. The MRI provides information regarding the status of the cochlear nerve within the cerebellopontine angle. To make the determination of cochlear nerve deficiency, the CT is examined for presence of the cochlear aperture at the base of the cochlea. If there is no opening to the cochlea, there is no cochlear nerve. If an opening is detected, the opening will be measured. If the opening is less than 1.4mm in diameter (normal is 1.4 – 3.0 mm, Huang et al., 2012; Kang et al., 2010; Miyasaka et al., 2010), cochlear nerve deficiency exists. Finally, the IAC will be measured and if less than 4 mm in diameter, cochlear nerve deficiency exists (Huang et al., 2012; Song et al., 2011). If the CT suggests a small cochlear nerve, the MRI sagittal oblique slices will be examined for evidence of the 4 cranial nerves. If the auditory nerve is not detected, cochlear nerve deficiency exists (Tamrazi et al., 2011). Detection of cochlear aplasia and complete cochlear ossification are more straightforward. For cochlear aplasia, a simple absence of the end organ on CT or MRI confirms the diagnosis. For complete cochlear ossification, a lack of T2 signal in the cochlea on MRI confirms the diagnosis.

Pre-operative Audiology, Speech Pathology, Psychological, and Educational Assessment.

Sound awareness behavioral testing

Infant-Toddler Meaningful Auditory Integration of Sound (IT-MAIS)

A Speech-Language pathologist (SLP) will perform assessments of communication skills in the child's main communication mode (oral, sign, other), including informal and parent-report assessments of communicative intent in very young children and an oral motor examination. For children for whom there are psychological concerns, a clinical psychologist familiar with developmental norms for children will perform tests of non-verbal IQ, appropriate to the child's age and development to determine the child's ability to accommodate to an ABI. An Educational Liaison, familiar with the educational services and system in the local area, will evaluate the child's intervention/educational programming.

ABI Surgery

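### Does waiving the amplification trial on CT evidence of ossification conflict with confirming ossification on MRI?

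*Protocol*

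**What the plan says.** Four places in the protocol bear on this.

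- **Inclusion criteria for subjects with and without a CI.** Every child needs "A diagnosis of one of the following, based on thin-slice MRI and CT". Complete post-meningitis ossification is one of the three diagnoses listed; cochlear aplasia and cochlear nerve deficiency are the others.
- **Inclusion Criteria for subjects without a CI.** The requirement is "Lack of audiological benefit after a three month appropriate amplification trial, except for" two groups. The first is "Post-meningitis subjects with CT evidence of complete ossification". The second is children with CT evidence of aplasia or nerve deficiency.
- **Diagnostic Imaging.** "All subjects selected for ABI will have already been studied by CT and MRI". On the diagnosis itself: "For complete cochlear ossification, a lack of T2 signal in the cochlea on MRI confirms the diagnosis". Aplasia may be confirmed on either scan. Nerve deficiency is worked up from CT measurements, with MRI as the further step.
- **Screening text after the Protocol Overview, and Table 1.** The text lists "Review of medical history, MRI and/or CT, pre-surgical evaluations, audiological evaluation, and speech language pathologist assessment". Table 1 has a single row for CT and MRI together, marked at screening.

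**The concern.** Diagnosis and waiver appear to rest on different scans. Ossification is the only one of the three diagnoses for which Diagnostic Imaging gives an MRI sign and nothing on CT, yet its exemption is written on CT. A literal reader could hold a child to the amplification trial although the diagnosis is confirmed, or waive the trial for a diagnosis that is not confirmed. The and/or in the screening text seems to make this worse, because a child might arrive with one scan only.

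What would be at stake is entry. A child held to a trial not yet done would wait up to three months. If the upper age limit of 72 months applies at entry (an assumption, since the protocol does not say), a child older than 72 − 3 = 69 months when the trial starts would become too old before it ended. With at most 10 subjects, one child handled inconsistently is 1/10 of the study.

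**Working it through.** The protocol has no figure to reproduce here, so the check is a comparison of the rules.

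**Step 1: are both scans secured?** The inclusion criterion, Diagnostic Imaging and Table 1 all name both scans. Only the screening sentence says and/or. That sentence has no verb. It lists what is looked at during screening and sets no entry condition. The protocol separately requires every entry criterion to be met, so a child with one scan cannot satisfy the imaging criterion. The single-scan cases drop out.

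**Step 2: with both scans done, where can the two rules diverge?** Take a post-meningitis child without a CI. Write MRI+ for the missing T2 signal and CT+ for CT evidence of complete ossification.

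| MRI | CT | Diagnosis confirmed | Trial waived | Effect |
|---|---|---|---|---|
| + | + | yes | yes | rules agree |
| + | − | yes by Diagnostic Imaging; arguable under a criterion based on both scans | no | trial required as written |
| − | + | no | yes, but idle | no qualifying diagnosis, so no entry |
| − | − | no | no | no entry |

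In the third row the waiver lifts one requirement but does not supply the missing diagnosis. Suppose instead that the MRI sign is read as sufficient but not necessary, so that CT can establish ossification. Diagnosis and waiver then both hold and agree. On neither reading does the waiver create an entry that the diagnosis does not support. Only the second row leaves handling open. These rows are logical patterns, not frequencies, and the documents give no rate of disagreement between scans.

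**Step 3: is the second row peculiar to ossification?** No. Aplasia may be confirmed on either scan but is exempted on CT evidence only. A child with aplasia seen on MRI and not on CT is in the same position: confirmed, and not exempt.

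**Step 4: is a narrower waiver coherent?** Yes. The three qualifying diagnoses are the same three that the exemptions name. If every confirmed diagnosis earned the exemption, the trial would bind nobody without a CI. Limiting the exemption to CT evidence is what leaves the trial a role. That is consistent with deliberate wording, though the text does not state the intention.

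**Step 5: what do the timing arguments add?** The delay runs from 0 months (trial already done) to 3 months. The 69-month threshold follows from the length of the trial and would apply to any child who had to complete it. It does not come from the difference between CT and MRI. A clash with the screening window cannot be shown either: the protocol says "The screening examinations may take place up to 3 months" and itself equates this with 12 weeks, nothing requires screening to precede the trial, and repeat screening is allowed at the investigators' discretion.

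**The case for a change.** The strongest case for acting is that the text does leave something unsaid. Diagnostic Imaging describes CT findings for nerve deficiency and accepts CT for aplasia, but gives no CT sign of complete ossification. The waiver therefore turns on a finding that the protocol never describes. Nor does it say what happens when the scans differ. These are eligibility rules, which belong in the protocol and would not be left to a SAP. The remedy would cost a few words: refer the waiver to Diagnostic Imaging and align the screening sentence with the other three places.

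Much of this is true. The and/or is inconsistent with the rest of the document, the CT sign is not named, and the MRI-positive, CT-negative child is not addressed explicitly. What does not stand is the step from there to a contradiction. One rule says how a diagnosis is confirmed; the other says which diagnosed children skip the trial. A child can satisfy both, and when the scans agree nothing is in doubt. A cross-reference would still leave the clinical team to decide which scan governs, which the Principal Investigators can already settle in their eligibility review.

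**Conclusion.** The concern does not call for a change. The and/or in the screening text is a clerical slip, overridden by a binding criterion that names both scans. The missing CT description is a detail that the investigators fill when they review each child's screening results. The waiver and the confirmation rule are compatible.

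What remains is one pattern (no CI, MRI positive, CT not positive), which arises for aplasia as well as ossification. Its effect is a wait of 0 to 3 months for that child and, if the age limit applies at entry, possible loss of eligibility for a child older than 69 months when the trial starts. How many such children there might be cannot be derived from the documents.

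No estimate, test or conclusion depends on the point. The section Endpoints and Statistics declares no endpoints, a maximum of 10 subjects and descriptive statistics only. The conclusion assumes that the inclusion criterion is applied as written, with both scans available for every child. It takes no view on which scan should govern. If the text is reopened for other reasons the wording could be tidied, but nothing in the study's results would change.

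### The Diagnostic Imaging section lets one below-cutoff CT measurement establish cochlear nerve deficiency, and no MRI result it states can withdraw that diagnosis

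*Protocol*

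**What the plan says.** All places are in the protocol.

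- **Inclusion criteria for subjects with and without a CI.** The child must have "A diagnosis of one of the following, based on thin-slice MRI and CT". The list that follows includes cochlear nerve deficiency, covering both aplasia and hypoplasia of the nerve.
- **Diagnostic Imaging, role of each scan.** CT is said to show the petrous bone and cochlea. For the nerve, "The MRI provides information regarding the status of the cochlear nerve within the cerebellopontine angle". Both scans will be on file: "All subjects selected for ABI will have already been studied by CT and MRI".
- **Diagnostic Imaging, CT rules.** No opening at the base of the cochlea is taken to mean no nerve. An opening that is present is measured: "If the opening is less than 1.4mm in diameter", deficiency is said to exist. Then: "Finally, the IAC will be measured and if less than 4 mm in diameter, cochlear nerve deficiency exists". The canal measurement is not expressly assigned to a scan; from its place in the text I read it as CT.
- **Diagnostic Imaging, MRI rule.** "If the CT suggests a small cochlear nerve, the MRI sagittal oblique slices will be examined for evidence of the 4 cranial nerves". One result is given a consequence: "If the auditory nerve is not detected, cochlear nerve deficiency exists". Nothing is said about a nerve that is detected.
- **Inclusion Criteria for subjects without a CI.** A three-month amplification trial is required, with an exception for CT evidence of cochlear aplasia or cochlear nerve deficiency.

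**The concern.** The section assigns the question of nerve status to MRI and then lets CT answer it. Each CT cutoff ends in a flat statement that deficiency exists, conditional neither on the other cutoff nor on MRI. The MRI step comes afterwards and can only agree. The inclusion criteria ask for a diagnosis resting on both scans, but nowhere does the protocol say what happens when they disagree.

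The diagnosis is a gateway to a retrosigmoid craniotomy and an electrode array on the brainstem in a child aged 2 to 6. The Subjects section also calls a CI the device of choice where there is a cochlea that can take one, so a mistaken nerve-deficiency label bears directly on which device a child is considered for. In a study of at most 10 subjects, one misclassified child would also weigh heavily in any descriptive summary.

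**Working it through.** The plan states no figure to reproduce on this point, since it has no endpoints and only descriptive statistics. The check is to write out the decision rule and see what MRI can change.

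**Inputs (Diagnostic Imaging).** Cochlear opening: absent, under 1.4 mm, or at least 1.4 mm. Internal auditory canal: under 4 mm, or at least 4 mm. Nerve on MRI: detected or not detected.

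**Rule as written.** Deficient = (no opening) OR (opening < 1.4 mm) OR (canal < 4 mm) OR (nerve not detected on MRI).

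**Enumeration.** There are 3 × 2 = 6 CT patterns, and 6 × 2 = 12 patterns with MRI.

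| CT pattern | Number of CT patterns | Nerve detected on MRI | Nerve not detected on MRI |
|---|---|---|---|
| No opening, either canal size | 2 | deficient | deficient |
| Opening present, at least one measurement below cutoff | 3 | deficient | deficient |
| Opening ≥ 1.4 mm and canal ≥ 4 mm | 1 | not deficient | deficient |

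So 5 × 2 = 10 of the 12 patterns have an abnormal CT. All 10 are labelled deficient, including the 5 in which MRI detects the nerve. Three of those 5 rest on a below-cutoff measurement; the other 2 rest on the absent opening. MRI alters the outcome only in the last row, and only by adding the label. Even there its role is uncertain, because the MRI reading is triggered by a CT that suggests a small nerve. These are counts of rule outcomes, not of patients.

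**What counts as disagreement.** A detected nerve is not in itself a conflict, because hypoplasia is eligible and a hypoplastic nerve can be visible. A rule requiring a below-cutoff or otherwise abnormal CT and an undetected nerve would label 0 of those 5 patterns, but it would wrongly shut out hypoplasia. The real conflict is narrower: CT below cutoff with a nerve that MRI shows to be normal. The protocol gives no MRI criterion separating a hypoplastic nerve from a normal one, so that case cannot even be recognised under the rule.

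**Side by side.** The inclusion criterion requires MRI and CT together. The Diagnostic Imaging rule is satisfied by CT, whatever MRI shows. For the discordant child the first calls for a judgement across both scans, while the second has already given the answer.

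**Comparison within the section.** The other two diagnoses do not share the problem. For aplasia, "For cochlear aplasia, a simple absence of the end organ on CT or MRI confirms the diagnosis"; complete ossification likewise has one named confirming feature. Neither opens a second-scan step and leaves it unfinished.

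**The case against.** The strongest reply is that CT is meant to flag and MRI to confirm. The section gives nerve status to MRI, says that CT may suggest a small nerve, and then sends the reader to MRI; that step has little purpose if CT is already final. Read with the two-scan inclusion criterion, this is a plausible account of the intent. It stands as to intent, but the text does not say it: deficiency is declared after each CT cutoff, and the result that would make confirmation meaningful, a normal nerve, has no stated consequence.

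It is also fair that other safeguards remain. Bilateral profound loss must be documented behaviorally, both scans are obtained, and the Principal Investigators review all screening results. A discordant MRI would therefore be in front of them. But the hearing criterion does not measure the nerve, and the review is given no rule for scans that disagree.

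A reader might infer something stronger from the exception for children without a CI: that the amplification trial is waived on CT alone, so that CT by itself carries a child to surgery. The protocol does not support that. The exception names CT evidence but does not say that CT suffices alone. It lifts one requirement and leaves in place the two-scan diagnosis required of every subject. Nor would changing the exception send the discordant child to the trial: once the imaging rule is corrected, a child with a normal nerve fails the diagnosis whether or not amplification was tried.

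**Conclusion.** The point holds as an inconsistency in a stated eligibility rule and should be corrected. As written, one below-cutoff CT measurement establishes nerve deficiency and the MRI rule cannot reverse it, contrary to the two-scan inclusion criterion and to the role the protocol itself gives MRI. The affected case is a single combination: CT below cutoff with a normal cochlear nerve on MRI. That child meets the diagnostic criterion on a literal reading but is not thereby enrolled, because the hearing-loss criterion and investigator review still apply.

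The size in patients cannot be stated. The documents give no accuracy figures for the cutoffs and no rate of discordant scans, and whether the cutoffs are clinically right cannot be judged from them. The conclusion assumes that the canal measurement is made on CT and that the statements of deficiency after each cutoff mean what they say. If confirmation by MRI was always intended, the fault is one of drafting, and the same edit cures it.

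**What to change.** **Diagnostic Imaging.** State that an opening under 1.4 mm or a canal under 4 mm on CT suggests nerve deficiency and must be confirmed on the MRI already obtained, by a cochlear nerve that is absent or hypoplastic. State that a nerve judged normal on MRI does not meet the nerve-deficiency criterion. The investigators should set the MRI definition of hypoplasia; the protocol does not contain one and this review cannot supply it. They should also say whether the absent-opening rule is subject to the same confirmation.

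**Inclusion Criteria for subjects without a CI.** As a conforming edit only, let the exception refer to nerve deficiency as determined by CT and MRI under Diagnostic Imaging. The exceptions for aplasia and complete ossification, and the route for children without a prior CI, stay as they are.

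**Cost.** No added scan or procedure. The real work is agreeing the hypoplasia definition. A few candidates with discordant scans may be excluded, or delayed while imaging is re-read.
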